
Objective Measures: (a) **Epigenetic (DNAm):** Peripheral blood specimens will be collected at baseline (gestation 12-22 weeks) and intervention week 12 (gestation of 24-34 weeks), as summarized in Table 1. The PD and/or RAs will arrange to meet participants to collect the blood and transport samples to the VCU School of Nursing's lab for DNA extraction.

Samples will be shipped to HudsonAlpha for DNA methylation assays. HudsonAlpha will use the following procedures for DNA methylation: genome-wide methylation patterns will be determined using the 450K HumanMethylation Chip (Illumina) according to the vendor's protocol. Briefly, DNA will be extracted from the blood samples using standard techniques (Puregene Isolation Kit; Qiagen). Following bisulfite conversion of the DNA, the methylation patterns of the 485,764 targets (including CpG islands, shores, open sea) interrogated in the 450K array will be determined. To verify the results of the 450K array for targeted regions of interest, single loci methylation-sensitive studies of bisulfite converted DNA will be conducted using standard methods.²⁰⁵ Gene-specific patterns of candidate genes chosen a priori will be closely examined. All samples will be coded prior to deliver to the testing labs. As methylation patterns vary from tissue to tissue, one concern is if the patterns present in white blood cells are reflective of the relevant cumulative epigenetic changes

involved in chronic depressive symptoms. Skepticism regarding the utility of blood for the assessment of conditions having brain/nervous system components has recently been diminished by the observation that comparable DNAm changes induced by environmental/social events occur in multiple tissues.⁷⁵ Based on these findings, Szyf²⁰⁶ noted that the results of recent investigations demonstrate that it is feasible to study behaviorally related DNA methylation signatures in peripheral cells²⁰⁶ (p.334). Given this supporting data, as well as the practical need to collect a minimally invasive specimen for study in this pregnant population, peripheral blood will be used to assess DNAm patterns. (b) Birth weight: At the postpartum visit, mothers will be asked to report the baby²⁰⁶s birth weight.

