Aim 3: Identify DNA methylation patterns associated with chronic depressive symptoms during pregnancy and investigate whether participation in the MOMS intervention targets these patterns: Drs. [name] and [name] will work closely and collaboratively to utilize statistical methods appropriate for this aim. Output from the 450K DNA methylation platform will be screened for process errors to ensure that the resultant data pass quality control standards (based on known sites having constant methylation, including genes influenced by X-inactivation) and then processed using the minfi Bioconductor package in the R programming environment.²¹⁰ While there is yet no established standard for the analysis of data from this platform, best practice recommendations have been published and will be followed.²¹¹⁻²¹⁴ CpG sites having a false discovery rate (FDR) <0.05 will be considered significant after multiple test correction. Sites recognized as differentially methylated will be evaluated using a suite of bioinformatic tools, such as the DAVID Functional Classification software program, to identify biological systems and/or functions that are consistently altered. Specifically, we will: (a) confirm genome-wide DNAm pattern differences between the non-intervention archival comparison groups: positive comparison (n=40) and negative comparison (n=40) over time (4 time points), using growth modeling methods; (b) identify within-group genome-wide DNAm pattern differences over time (pre/post the intervention) using paired t-tests (n=40); and (c) identify overlapping DNAm differences among the three groups (n=120) and prioritize CpG sites to further evaluate based upon specific candidate genes that have received attention in the literature in relation to depressive symptoms and mindfulness-based interventions, including: glucocorticoid receptor (GR) Nr3c1, its promoter region NGFI-A, and GR chaperone protein FKBP5;^{84,86-88} brain-derived neurotrophin factor (BDNF) and its receptor TrkB;⁸⁹⁻⁹² and estrogen receptor-alpha and related genes HP1BP3 and TTC9B.⁹³⁻⁹⁶ These steps are pictured in Figure 3.

The goal of these confirmatory and exploratory analyses is to determine whether DNA methylation patterns predict treatment response and whether the intervention has targeted DNA methylation differences identified in the steps outlined

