(a) positive comparison group (n=40): pregnant women with clinically relevant depressive symptoms receiving the UC; and, (b) negative comparison group (n=40): pregnant women without clinical depressive symptoms. The timelines of these studies align well; as of May 2015, the study has enrolled approximately 135 women (50% AA) with ~15% of the sample endorsing depressive symptoms (unpublished data). Data collection from the total expected sample (n=220) will be completed by early 2017, at which point the proposed study will be ready to derive the comparison groups for analysis. To facilitate longitudinal comparisons across the two studies, the pre-/post-intervention data for the proposed study will correspond to data collected early in the second trimester of pregnancy (approximately 12-22 weeks gestation) and late in second trimester/ early in third trimester of pregnancy (approximately 24-34 weeks gestation) respectively, in the comparison study, represented in Figure 2. This analysis is fully described in section D.8.2. Although the lack of a concurrent randomized control group presents a threat to statistical conclusion and internal study validity, the use of this archival comparison group data is important because it contributes rich longitudinal comparison data of extensively phenotyped pregnant women. Further, use of archival comparison group data allows for full exploration of our primary aim (feasibility and acceptability of the pilot MOMS intervention) with a large enough sample size (total n=120; n=40 participants of MOMS intervention; n=40 positive comparison group; n=40 negative comparison group) to also explore preliminary effects, which increases statistical conclusion validity (reducing Type II error), maximizes flexibility in the budget of the R15 mechanism, and contributes important data for the development of future studies.

2. * Describe how you have access to the data/specimens:

[name], co-I on this study, is the PI on the study which will provide the deidentified archival data.

3. *

Describe any identifiers or coded information that will be obtained that can be linked directly or indirectly to the identity of participants:

n/a-- data will be completely deidentified

4. * Did individuals provide consent for research when the data / samples were originally collected?

Yes
 No

5. If yes, did the consent allow for sharing of the data:

Yes
 No

ID: MS8_HM20006941

[View: SF - Internet Data Collection Details](#)

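### Aim 3 names no test of methylation change in MOMS against change in depressed usual-care women, so the tests as named cannot separate an intervention effect from change over gestation

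*Combined protocol and SAP*

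**What the plan says.** All steps are in the Research Description, Data Analysis Plan, Aim 3.

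- **Goal:** to determine, among other things, "whether the intervention has targeted DNA methylation differences identified in the steps outlined".
- **Step (a)** covers the archival groups only: "positive comparison (n=40) and negative comparison (n=40) over time (4 time points), using growth modeling methods". MOMS is not in this model.
- **Step (b):** "identify within-group genome-wide DNAm pattern differences over time (pre/post the intervention) using paired t-tests (n=40". No comparator enters.
- **Step (c):** "identify overlapping DNAm differences among the three groups (n=120"), followed by prioritising sites in listed candidate genes. No model, contrast, direction or decision rule is given.
- **Error control:** "CpG sites having a false discovery rate (FDR) <0.05 will be considered significant after multiple test correction".

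The timing is under Objective Measures: "Peripheral blood specimens will be collected at baseline (gestation 12-22 weeks) and intervention week 12 (gestation of 24-34 weeks"). MOMS therefore contributes two methylation occasions.

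Specific Aim 3 and the study design statement both say that methylation will be compared with the archival groups, but neither names a test. Aim 2 has a group-by-time mixed model, described for psychological symptoms and not for methylation. Existing Data/Specimen Details, item 1, discusses the longitudinal comparison across the two studies and adds: "This analysis is fully described in section D.8.2". That section is not in the supplied text.

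**The concern.** A one-group pre/post test compares the second trimester with the late second or early third trimester in the same women. Any methylation change that comes with advancing pregnancy appears in it exactly as an intervention effect would. The remedy is to subtract the change seen over the same gestational windows in depressed women who did not receive MOMS. No named step does this.

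Step (c) may be meant to fill the gap, but as worded it does not say what is compared with what. One natural reading is that a site counts if it is significant in (a) and also in (b). On that reading, an intervention that holds methylation steady while usual-care women drift shows no pre/post change and fails step (b). An intervention that does nothing lets MOMS drift along with usual care and passes. Whether this happens depends on which group drifts, and the documents are silent on that.

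At stake is the interpretation of Aim 3: which sites are reported as targeted by MOMS, and which estimates go forward to the next study.

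**Working it through.** **The plan's own figure.** The Aim 3 sample size is 40 + 40 + 40 = 120, as stated. No power, effect size or SD of methylation change is given for Aim 3, so nothing else can be reproduced.

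**Inputs from the documents.** 40 women per group. Attrition of 20-40% (sample size justification) leaves 32 or 24 MOMS pairs. An archive of 220 with about 15% depressed gives 0.15 × 220 = 33 positive women, if that share holds at full enrolment.

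**Assumptions, not in the documents.** Drift of 0.5 SD, in SDs of within-woman change (0.8 SD as a check); normal change; two-sided tests at per-site p<0.05. Step (a) is simplified to a two-sample t-test on change, positive versus negative. Step (b) is a one-sample t-test on MOMS change. Step (c) is read as significant in both.

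**Component rejection rates (noncentral t, 40 per group, 0.5 SD).**
- Two-sample t, noncentrality 0.5/√(1/40 + 1/40) = 2.24: 59.8%.
- One-sample t, noncentrality 0.5 × √40 = 3.16: 86.9%.
- Either test with no true difference: 5%.

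Steps (a) and (b) use different women, so the overlap rate is the product of the two. The direct contrast is a two-sample t-test on change, MOMS versus positive.

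| Pattern (change: positive / negative / MOMS) | Overlap, direction ignored | Direct contrast |
|---|---|---|
| Depressed drift, halted (0.5 / 0 / 0) | 0.598 × 0.05 = 3.0% | 59.8% |
| Depressed drift, inert (0.5 / 0 / 0.5) | 0.598 × 0.869 = 52% | 5% |
| Mirror, restored (0 / 0.5 / 0.5) | 0.598 × 0.869 = 52% | 59.8% |
| Mirror, inert (0 / 0.5 / 0) | 0.598 × 0.05 = 3.0% | 5% |

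**If MOMS must change opposite to the step (a) difference.** In the first pattern, halted falls to 1.5% and inert to about 0.001%. In the mirror pattern, restored stays at 52% and inert is 1.5%.

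**Sensitivity.**
- At 0.8 SD, halted drift gives an overlap of 4.7% against 94% direct; in the mirror pattern, restored gives 94% for both.
- At 0.5 SD with 24 MOMS, 33 positive and 40 negative women, halted drift gives 2.8% against 45%, and inert gives 36% against 5%.
- A stronger growth model in step (a) cannot lift the halted row above 5%, because step (b) rejects there only at its own alpha.

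**Effect of a stricter threshold.** At p<1e-4 the direct contrast detects a 0.5 SD difference in 3.9%, and the overlap detects a halted drift in essentially none.

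**Selection at step (a) sites.** The positive group would both select these sites and serve as comparator. With an inert intervention and no drift, the direct contrast has p<0.05 in about 18% of sites that step (a) selects at p<0.05, and in about 41% of those it selects at p<0.001. With 0.5 SD drift these are about 5% and 10%.

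**The case against.** **The comparison is intended and may be specified elsewhere.** Specific Aim 3 states the intent to compare, step (c) speaks of three groups, and neither Figure 3 nor section D.8.2 could be seen. This stands as a limit: if a contrast is stated there, copying it into Aim 3 settles the point. A joint three-group test would not settle it alone. At 0.8 SD an F-test on change rejects in 96.3% both when the drift is halted and when the intervention is inert, so the contrast must still be named.

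**A reader might infer that an effect that halts drift would be missed, and that no direction rule could rescue the overlap.** The documents do not support this. It needs both the intersection reading of step (c) and the pattern in which only depressed women drift. In the mirror pattern the overlap works nearly as well as the direct contrast. Aim 3 speaks of patterns associated with chronic symptoms and does not posit a halted drift.

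**The rates are not at the plan's threshold.** This stands. They compare tests at a single site and are most relevant to the candidate genes. Genome-wide, both approaches have little power.

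**It is a pilot with a disclosed limitation.** The plan says that "the lack of a concurrent randomized control group presents a threat to statistical conclusion and internal study validity" and claims no power for effectiveness. That limits what can be concluded, but a pilot meant to supply effect-size estimates still needs the estimate to be of the controlled change.

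**A reader might infer badly mismatched draw intervals in the archive from the gestational windows.** Those windows are approximate, apply to both studies, and are scheduled in Figure 2, which is not shown. No such mismatch can be claimed.

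**Conclusion.** The concern holds in conditional form. On the supplied text, the tests named for Aim 3 cannot separate an intervention effect from change over gestation. That conclusion rests on the wording alone and needs no assumed drift.

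The size of the consequence is conditional on the intersection reading, the simplified step (a), per-site p<0.05 and an assumed 0.5 SD drift with 40 per group. If only depressed women drift, a fully halted drift is flagged in about 3% and an inert intervention in about 52% when direction is ignored, against 60% and 5% for the direct contrast. If only non-depressed women change, a restored change is flagged in 52% against 60%. The documents do not say which pattern applies, so neither a missed effect nor false credit can be called the expected outcome. The point should be fixed before analysis; confidence is medium because Figure 3 and section D.8.2 are unseen.

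**What to change.** In Aim 3, step (c):

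1. Name a per-CpG group-by-time contrast, MOMS versus the positive comparison group, on the two aligned occasions, adjusted for gestational age at draw.
2. Control FDR at 0.05 genome-wide and, as a separate family, within the a priori candidate genes.
3. At sites found in step (a), report this contrast with its 95% CI and its direction relative to the step (a) difference. Do not apply a nominal 0.05 test there, because the positive group both selects and tests.
4. Label the paired t-tests descriptive.
5. State that confounding by study and by assay batch may remain, since the groups are not randomised.

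**Cost.** Wording only; no new samples. Precision falls: at 40/40 the standard error is √(1/40 + 1/40) ÷ √(1/40) = 1.41 times that of the paired test. The 95% CI half-width is 1.99 × √(1/40 + 1/40) = 0.45 SD, rising to 0.50 SD at 32/33 and 0.54 SD at 24/33. Few or no genome-wide sites may be declared, so the usable output would be the interval estimates and the candidate-gene results, which suits a pilot.

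### Aim 3 step (b) tests pre/post methylation change in peripheral blood by a plain paired t-test, so a within-woman shift in blood-cell mix cannot be told apart from a methylation change

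*Combined protocol and SAP*

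**What the plan says.** All references are to Research Description, item 4, unless stated.

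- **Samples.** Objective Measures (a): "Peripheral blood specimens will be collected at baseline (gestation 12-22 weeks) and intervention week 12 (gestation of 24-34 weeks"). For the assay, "DNA will be extracted from the blood samples using standard techniques", and the array reads "the methylation patterns of the 485,764 targets".
- **Tissue.** The same paragraph raises one source-of-DNA issue: "As methylation patterns vary from tissue to tissue, one concern is if the patterns present in white blood cells are reflective" of changes relevant to depression. That concerns blood as a stand-in for other tissue. The mix of cells within blood is not discussed.
- **Test.** Data Analysis Plan, Aim 3, step (b): "identify within-group genome-wide DNAm pattern differences over time (pre/post the intervention) using paired t-tests (n=40"). The decision rule is "CpG sites having a false discovery rate (FDR) <0.05 will be considered significant after multiple test correction".
- **Processing.** Output is "processed using the minfi Bioconductor package in the R programming environment". The plan adds that "best practice recommendations have been published and will be followed", without saying what those recommendations contain.
- **Groups.** Step (a) compares the two archival groups over time. Step (c) looks for overlap in differential sites among the three groups and then prioritises candidate genes. Comparison Group Data lines up the archival samples with the same two gestational windows.
- **Attrition.** Study Population, item 3, expects 20-40%.

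**The concern.** DNA taken from blood is a mixture. At each site the array reports an average over the cell types present, weighted by their proportions. If those proportions move between the two draws, the average moves at every site where cell types differ, even if no cell has changed its methylation.

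A paired t-test removes stable differences between women. It does not remove a shift that happens within women between draws, which is exactly what it measures. Multiple-testing control does not help either: the mean change at such a site is real, and only its cause would be misread.

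Aim 3 asks whether MOMS targets depression-related methylation patterns, and its output is meant as preliminary data for later studies. Sites that only mark cell mix or advancing gestation could enter the pathway tools and the candidate list as intervention effects.

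**Working it through.** **The plan's own figure.** No effect size, SD or power lies behind n=40 in Aim 3, so there is nothing to reproduce beyond 3 x 40 = 120. Attrition of 20-40% leaves 40 x 0.8 = 32 to 40 x 0.6 = 24 pairs.

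**Single site.** Let the mean shift in one cell fraction be Δ, the methylation difference between cell types D, the SD of within-woman change s, and the number of pairs n. With no methylation change in any cell, the expected change is Δ x D, and t = (Δ x D / s) x √n on n - 1 df. None of Δ, D or s is in the documents. I assume Δ = 2, 5 or 10 points, D = 0.2-0.5 and s = 0.02-0.03. Tests are taken as two-sided.

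| Shift | Pairs | Weakest case (D 0.2, s 0.03) | Strongest case (D 0.5, s 0.02) |
|---|---|---|---|
| 2 points | 24 | t = 0.65, p = 0.52 | t = 2.45, p = 0.022 |
| 2 points | 32 | t = 0.75, p = 0.46 | t = 2.83, p = 0.008 |
| 5 points | 24 | t = 1.63, p = 0.12 | t = 6.12, p = 3e-6 |
| 5 points | 32 | t = 1.89, p = 0.069 | t = 7.07, p = 6e-8 |
| 10 points | 24 | t = 3.27, p = 0.003 | t = 12.25, p = 1.5e-11 |
| 10 points | 32 | t = 3.77, p = 0.0007 | t = 14.14, p = 5e-15 |

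The last entry, for example, is 0.10 x 0.5 = 0.05; 0.05 / 0.02 = 2.5; 2.5 x √32 = 14.14. At 2 points, only D = 0.5 with s = 0.02 falls below 0.05.

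The table treats every woman as shifting equally. If shifts vary with an SD of 5 points, s becomes √(s² + (0.05 D)²). For D = 0.5 and s = 0.02 that is √(0.0004 + 0.000625) = 0.032. At 32 pairs the 10-point case then gives t = 8.83 (p = 6e-10) and the 2-point case t = 1.77 (p = 0.087).

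**Under the plan's FDR rule.** These are single-site p-values, so a simulation applied Benjamini-Hochberg at 0.05 to 20,000 sites. At 2,000 of them cell types differed by 0.1-0.8. The residual SD of change was 0.03, the SD of the shift 5 points, with 40 runs per setting and no methylation change in any cell type. Mean false hits:

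| Pairs | No shift | 2 points | 5 points | 10 points |
|---|---|---|---|---|
| 40 | 0.05 | 60 | 1,331 | 1,936 |
| 32 | 0.03 | 35 | 952 | 1,877 |
| 24 | 0.03 | 0.1 | 523 | 1,762 |

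Regressing the change on the change in cell fraction and testing the intercept gave 0.1 or fewer in every setting. Testing the difference in change against a comparison group with the same shift gave 0.15 or fewer.

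**Why gestational age should not join visit in the model.** Draws are about 12 weeks apart in each woman, so the two are nearly the same variable. With 32 pairs, baseline uniform over 12-22 weeks, an interval of 12 weeks with SD 0.5-1.5, and within-woman correlation 0.3-0.8 (all but the window assumed), adding gestational age multiplies the SE of the visit effect by about 3-6 in a random-intercept model and about 8-25 in a regression of paired differences.

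**Precision cost of one cell fraction.** At sites where cell types do not differ, the SE of the adjusted change rises by about √(1 + (mean shift / SD of shift)²). That is √2 = 1.41 when the mean equals the SD, 1.08 at 2 points and 2.24 at 10 points with an SD of 5.

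**The case against.** The strongest reply is that the plan promises to follow published recommendations before step (b), and a paired t-test can be run on values already corrected for cell mix. That is possible. A reader might infer that the plan rules out such a correction; it does not. But the plan does not state one either, and the recommendations' content is not given. What stands is that the handling of cell mix is unspecified and the one test named has no term for it.

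Second, the archival groups sampled in matching windows are a natural control: a group-by-time contrast cancels any shift common to both groups. This is right, and it belongs in the fix. Aim 2 specifies that interaction; Aim 3 step (c) asks only for overlapping sites.

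Third, a reader might infer that cell-mix sites *would* be reported as targeted. The documents do not support that. Step (c) also requires overlap and then prioritises candidate genes, and a gestational shift common to both archival groups would not by itself create a difference between them in step (a). The supportable word is *could*.

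Fourth, the shift is assumed, and small shifts do little. A reader might also hold the larger effects against a genome-wide threshold near 1e-7 (0.05 / 485,764); that is not the plan's rule, which is FDR below 0.05.

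Finally, the text says peripheral blood. That unfractionated blood is used is inferred from the EDTA tubes and the absence of any separation step.

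**Conclusion.** The point holds as a statement about what the named analysis cannot separate. It is not evidence that a particular bias will occur. As written, step (b) would attribute a change in cell mix to methylation, and step (c) names no between-group test that would remove a shared gestational change.

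The size depends entirely on assumed inputs. With 24-32 pairs, D of 0.2-0.5 and s of 0.02-0.03, a 2-point shift mostly gives p above 0.05, while 5-10 points gives p from about 0.1 to below 1e-14. In the simulation, false FDR hits at those pair counts range from almost none at 2 points with 24 pairs to about 1,900 of 20,000 at 10 points with 32 pairs. Because the aim is partly exploratory and the output preliminary, this is a cheap improvement, not a fatal flaw.

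**What to change.** 1. **Step (b):** replace the plain paired t-test by a per-site model of within-woman change, with a visit effect and a random intercept per woman, adjusted for cell-type proportions estimated from the same arrays. Do not add gestational age alongside visit.
2. **Step (a):** use the same cell-proportion covariates.
3. **Step (c):** add a test of the difference in change (group by time) between MOMS and the archival positive comparison group over the matching gestational windows.
4. **Reporting:** give unadjusted results beside the adjusted ones.

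Parts 1 and 3 do different jobs. Cell adjustment separates composition from methylation. The group contrast removes a gestational change common to both groups, and only that.

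**Cost.** No new blood samples and little extra analysis, provided the archival data include the array output needed to estimate proportions. Some precision is lost: an SE about 1.4 times larger when the mean shift equals its SD, more if the shift is large relative to its spread. The near-zero false hits after adjustment assume the cell fraction is known without error; estimated fractions will leave some residue. Any effect of MOMS that acts through cell mix drops out of the adjusted estimate, which is why both results should be shown.
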